1.3 Known and Potential Risks and Benefits

There is no expectation of clinical benefit for the patients who volunteer to participate in this study. The risks of administering MYK-491 to humans are unknown, but based on nonclinical observations and the administration to healthy volunteers, MyoKardia considers that it can safely be administered if patients are carefully observed. Safety testing in other mammalian species demonstrates that dose-limiting toxicity is related only to on-target exaggerated pharmacology with development of myocardial ischemia and heart failure at high doses and after prolonged exposures. No off-target adverse effects were observed in the toxicology studies. The initial doses of MYK-491 given in this study have already been

administered as a single dose to healthy volunteers in a previous study (MYK-491-001) and shown to be well-tolerated (see above [Section 1.2](#)).

In Part 1 (single-ascending dose), patients will be admitted to the clinical research facility for dosing and will remain confined for a total of 3 days and 3 nights for each of 3 or 4 dosing periods or longer if the Safety Review Committee (SRC) believes it is important to assure the safety of the patients or to obtain robust PK and/or PD data. In no case will the patients remain confined for more than 5 days after the administration of the last dose of MYK-491.

In Part 2 (multiple-ascending doses), patients will be confined to the clinical research facility for the duration of the dosing and 2 days after dosing unless they have an ICD. Patients with the ICD will be observed frequently either in the research facility or by a home health nurse for all of the dosing, and the collection of the study parameters (plasma samples, safety labs, vital signs, and TTEs). Thus, all patients will be under close supervision, and the clinic staff will be responsible for the ongoing safety and well-being of the patients while they are confined for during the dosing periods. If a home health nurse is utilized, the nurse and site will be in daily communication to ensure safety. The initial dose for the MAD Cohort is predicted to reach exposures that have previously been observed in patients in Part 1. [REDACTED]

[REDACTED]

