3.1 Primary Objective

The primary objective of the study is to establish preliminary safety and tolerability of single- and multiple-ascending oral doses of MYK-491 in ambulatory patients with stable HFrEF.

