10 EVALUATION, RECORDING, AND REPORTING OF ADVERSE EVENTS

10.1 Definitions

10.1.1 *Adverse Event*

An AE is any untoward medical occurrence, or the deterioration of a preexisting medical condition (other than the condition that is being treated by the study) associated with the use of a study medication in humans, whether or not it is considered related to the study medication. An AE (also referred to as an adverse experience) can, therefore, be any unfavorable and unintended sign (eg, tachycardia, enlarged liver, clinically important abnormal laboratory result or diagnostic procedure), patient-reported symptom (eg, nausea, chest pain), or evidence of any disease activity temporally associated with the use of a study medication, whether or not related to the study medication.

In clinical studies, an AE can include an undesirable medical condition occurring at any time after the patient has signed informed consent, including run-in or washout periods, even if no specific treatment has been administered.

Preexisting medical conditions (other than natural progression of the disease being studied) judged by the investigator or patient to have worsened in severity or frequency or changed in character during the protocol-specified AE reporting period will be reported as AEs or SAEs as appropriate.

Imaging-based assessments of decrease in contractility are not considered AEs unless associated with symptoms or signs of clinical concern on the part of the investigator. Such events should be categorized as an AE defined in terms of those symptoms or signs.

An AE or SAE can also be a complication that occurs as a result of protocol-mandated procedures (eg, invasive procedures such as biopsies).

For MyoKardia to collect additional information about clinically important laboratory results or diagnostic tests (eg, blood, ECG, imaging), at a minimum, the following abnormalities should be captured on the AE eCRF:

- Any test result that meets the definition of an SAE
- Any clinically important test abnormality that suggests a disease and/or organ toxicity that has worsened or is new (eg, > 3 times deviation from the upper or lower limit of the analyzing laboratory reference range, or as otherwise specified in the protocol)
- Any test abnormality that requires the patient to have study medication discontinued or interrupted or in the clinical judgment of the investigator

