- Any test abnormality that requires the patient to receive specific corrective therapy, close observation, more frequent follow-up assessment, or further diagnostic investigation

The term AE is used generally to include any AE whether serious or nonserious.

10.1.2 *Serious Adverse Event*

An SAE is an AE that fulfills 1 or more of the following criteria in the opinion of the investigator or MyoKardia:

- Results in death
- Is immediately life-threatening (places the patient at immediate risk of death from the event as it occurred)
- Requires in-patient hospitalization or prolongation of existing hospitalization
- Results in persistent or significant disability or incapacity or substantial disruption of the ability to conduct normal life functions
- Results in a congenital abnormality or birth defect
- Is an important medical event that may not result in death, be life-threatening, or require hospitalization, but may be considered an SAE when, based upon appropriate medical judgment, it may require medical or surgical intervention to prevent 1 of the outcomes listed above

10.2 *Events NOT Meeting the Definition of an Adverse Event*

If an event is not an AE then it cannot be an SAE, even if the event outcome meets the definition for seriousness defined by the criteria in [Section 10.1.2](#). Instances where an event is not an AE include

- Medical or surgical procedure (eg, endoscopy, appendectomy): the condition that leads to the procedure is the AE
- Situations in which an untoward medical occurrence did not occur (social and/or hospital admission/extension for convenience)
- The disease/disorder being studied or expected progression, signs, or symptoms of the disease/disorder being studied, unless more severe than expected for the participant's condition
- Anticipated day-to-day fluctuations of preexisting disease(s) or condition(s) that are present or detected at the start of the study that do not worsen

10.3 *Adverse Event Reporting and Descriptions*

10.3.1 *Reporting Period and Follow Up*

All AEs will be reported from the time the patient provides informed consent through the last visit or 30-day period after last dose of study medication, whichever is longer. SAEs occurring after providing informed consent but before the first dose of study medication will

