be reported as SAEs only if they are considered related to protocol or study procedure. Preexisting medical conditions that increase in severity from the first dose of study medication will be reported as AEs. Preexisting medical conditions that increase in severity after providing informed consent but before the first dose of study medication will be reported as medical history. Overdose should be reported using the same method as SAE reporting.

Any AEs that are unresolved at the patient's last visit in the study are to be followed by the investigator until resolved or stabilized and are considered irreversible, or the patient has died.

MyoKardia retains the right to request additional information for any patient with ongoing AE(s)/SAE(s) at the end of the study if judged necessary.

All SAEs regardless of causality will be reported by the investigator or designee to MyoKardia or its designee within 24 hours of knowledge of the event. All follow-up information for previously reported SAEs will also be reported to MyoKardia or its designee within 24 hours of knowledge. Deaths and SAEs occurring beyond this timepoint and considered related to study medication or study procedure must also be reported.

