investigator may add extra 12-lead ECG safety assessments if there are any abnormal findings or if the investigator considers it required for any other safety reason. If the patient has any signs or symptoms suggestive of possible cardiac ischemia, additional ECGs should be obtained. These assessments should be recorded as unscheduled assessments.

- ^h Changes in a Baseline condition after the ICF is signed but before IMP is administered are recorded on the medical history eCRF unless the change is considered an AE related to a study procedure. All changes that occur after administration of the study medication are recorded as AEs.
- ⁱ A full TTE must be performed at Screening. Two TTEs will be performed during screening, no fewer than 7 days apart. Eligibility must be confirmed by core laboratory for both TTEs. Effort should be made for the second TTE to be performed as close to time of dosing as is feasible, taking into account core laboratory processing time and patient availability. After the Screening assessment, abbreviated TTEs will be performed. It is important that the TTEs are completed as close as possible to the scheduled time. TTEs will be evaluated locally for changes that might affect dosing decisions for others in the cohort, but the official reading will be done centrally by experts in a core laboratory in a blinded manner with results provided to the SRC. The SRC may modify the timing of the TTEs after the initial cohort so that for each subsequent cohort a TTE is obtained at the time of the predicted peak pharmacological effect. This will be based on the PK and TTE profiles from the previous cohorts. If appropriate, the SRC can request up to 2 additional TTEs be obtained.

- ^k ECG telemetry will be initiated at least 1 hour predose and continued through at least 48 hours. Additional monitoring may be needed based on data and/or patient's tolerance to the treatment.
- ^l Blood sample for HIV, HCV, and HBV will be collected at Screening.
- ^m Pregnancy tests, urine or blood based on the policy of the local institution or regulating Health Authority (eg, requirement for serum-based testing in the UK), should be performed on all females at Screening, Day-1, and Follow-up.
- ⁿ FSH tests will be included for potentially postmenopausal women.

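### The protocol's rules on whether worsening heart failure after dosing counts as an adverse event contradict each other, and heart failure is a toxicity anticipated from the animal data

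*Combined protocol and SAP*

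**What the plan says.** Five pieces of text decide whether a change in a patient's heart failure is recorded as an AE.

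- **Section 10.1.1, opening definition.** An AE includes "deterioration of a preexisting medical condition (other than the condition that is being treated by the study"; the parenthesis closes there, with no qualifier.
- **Section 10.1.1, later paragraph.** Worsened preexisting conditions are AEs, and only the natural progression of the studied disease is left out.
- **Section 10.2.** Among the things that are not AEs is "The disease/disorder being studied or expected progression, signs, or symptoms of the disease/disorder being studied, unless more severe than expected". The sentence then ties the expectation to the individual participant, but nothing says what is to be expected. The section also states: "If an event is not an AE then it cannot be an SAE", even where the outcome would meet a seriousness criterion.
- **Section 10.3.1.** "Preexisting medical conditions that increase in severity from the first dose of study medication will be reported as AEs". There is no exception for heart failure.
- **Schedule footnotes** (Tables 2, 3 and 4 for Part 1, Table 5 for Part 2), on changes in a Baseline condition: "All changes that occur after administration of the study medication are recorded as AEs". Again there is no exception.

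Three other places give the context. Section 3.1 says "The primary objective of the study is to establish preliminary safety and tolerability", and Section 11.2.1 lists treatment-emergent AEs and SAEs first among the primary safety measures. Section 1.3 reports, from testing in other mammalian species, that "dose-limiting toxicity is related only to on-target exaggerated pharmacology with development of myocardial ischemia and heart failure at high doses and after prolonged exposures". Section 4.5 sends suspected ischemia, ventricular arrhythmia and troponin elevation to independent adjudication; worsening heart failure is not listed.

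**The concern.** The disease under study and an anticipated on-target harm are the same condition. A carve-out for the studied disease therefore falls on an event that the safety objective needs to count. Section 1 describes this trial as the first use of the drug in patients with heart failure.

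Section 10.2 asks the investigator to decide whether a worsening was to be expected before it is recorded at all. In a randomized, placebo-controlled study that order is backwards. Events should be recorded alike in both arms, attribution should be judged separately, and the placebo data should show the background rate.

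Two consequences follow. First, sites that follow different sections will classify the same event differently, so the incidence of heart failure AEs by dose depends partly on which text a site reads. Second, the individual stopping criteria (Sections 4.2.1 and 4.2.4) and the ad hoc Safety Review Committee (SRC) criteria (Sections 4.2.2 and 4.2.5) refer to drug-related SAEs. An event held not to be an AE cannot reach them by that route. No other individual stopping criterion names worsening heart failure, and the echocardiographic criteria concern increases in ejection time or contractility. A fall in contractility on imaging is not an AE without symptoms or signs of clinical concern (Section 10.1.1).

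**Working it through.** The plan has no figure to reproduce: Section 11.1 plans no hypothesis test and gives no power calculation. The check is to apply each rule to the same two events after dosing: (a) symptomatic worsening of heart failure without admission, and (b) an admission for heart failure.

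| Rule | (a) Symptoms worsen | (b) Admission |
|---|---|---|
| 10.1.1, opening definition | Deterioration of the studied condition is outside the definition | Same; if not an AE, then by 10.2 not an SAE |
| 10.1.1, later paragraph | AE unless called natural progression | AE or SAE unless called natural progression |
| 10.2 | AE only if worse than expected for that patient | Same; otherwise not an SAE despite the admission |
| 10.3.1 | AE | AE; SAE because hospitalization is a seriousness criterion (10.1.2) |
| Footnotes, Tables 2 to 5 | AE | Same as 10.3.1 |

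The rows give three different answers: excluded, recorded depending on judgement, and always recorded. No section says which prevails.

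**Weight of one event.** A Part 2 cohort of 8 has 6 active and 2 placebo patients (Section 4.1.2), so one event among the active patients is 1/6 = 16.7 percentage points. If a cohort expands to 24, the active group is 24 × 3/4 = 18, and one event is 1/18 = 5.6 points. This is the leverage of a single event, not an estimate of how many would be lost.

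**Illustration of scale.** Let *p* be the true risk of worsening heart failure on active drug and *s* the share of such events recorded as AEs. Both are assumptions; the documents give neither. The chance of at least one recorded event among 6 active patients is 1 − (1 − *p·s*)^6.

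| *p* | *s* = 1 | *s* = 0.5 |
|---|---|---|
| 5% | 26.5% | 14.1% |
| 10% | 46.9% | 26.5% |
| 20% | 73.8% | 46.9% |
| 30% | 88.2% | 62.3% |

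For *p* = 10%: 1 − 0.90^6 = 46.9% and 1 − 0.95^6 = 26.5%. At *s* = 0 the chance is zero, but that requires a site to apply the opening parenthesis of 10.1.1 and disregard everything else.

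**The case against.** A reader might infer that the protocol leaves worsening heart failure out of safety reporting altogether. The text does not support that. Under Section 10.2, worsening beyond what is expected for the patient remains an AE. These patients are selected as stable: heart failure medication unchanged for at least 2 weeks, no heart failure hospitalization within 90 days. They are observed around single doses or over 7 days of double-blind dosing. A decompensation or admission in that setting would naturally be judged worse than expected. Section 10.1.1 also counts untoward signs, symptoms and evidence of disease activity, and Section 10.3.1 and the footnotes would capture the event.

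Four other strong readings also fail.

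- *Heart failure is an established toxicity of the drug in patients.* The finding is nonclinical, at high doses and after prolonged exposure. For patients, Section 7.4 speaks of ischemia.
- *Losing one SAE always removes an SRC review.* The trigger also requires that the SAE be drug-related and that none such has occurred on placebo. An investigator who blames the disease would probably answer no on causality in any case, so a recording rule alone would not restore the trigger.
- *The SRC would escalate without seeing the harm.* Examination, vital signs, weight, echocardiography and concomitant therapy are collected whatever the AE status, as is NT-proBNP in Part 2. Scheduled SRC reviews use unblinded summaries, although their content is not specified.
- *Section 10.3.1 and the footnotes already state the full rule needed.* They do not mention heart failure hospitalization or say that presumed natural progression is irrelevant.

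These points narrow the concern but do not remove it. The contradiction remains, the expectation is undefined, and collected weights and echocardiograms do not put an event into the AE/SAE tables. The stability of the patients also shows that an exclusion for expected progression has little legitimate work to do over so short a period.

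**Conclusion.** The concern holds as an internal contradiction, not as a blanket omission. Sections 10.1.1, 10.2 and 10.3.1 and the footnotes to Tables 2 to 5 give incompatible instructions for worsening heart failure after dosing. Section 10.2 makes recording depend on an undefined judgement and closes the route to SAE status. The effect on the primary AE/SAE measure is direct; the effect on the drug-related-SAE criteria is possible but conditional on causality and, for the SRC criterion, on the placebo experience.

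The size of any under-recording cannot be derived from the documents. The detection probabilities rest on assumed risks and recording shares and show only that cohorts of 6 active patients have little room to lose an event. The conclusion itself rests on the wording alone.

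**What to change.** Reconcile Sections 10.1.1, 10.2 and 10.3.1 and the footnotes to Tables 2, 3, 4 and 5 into one recording rule:

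- New or worsening heart failure signs or symptoms, or a heart failure hospitalization, after the first dose are recorded as an AE, and as an SAE if a seriousness criterion in 10.1.2 is met, whether or not they are thought to be natural progression.
- Causality is assessed separately, by the question already in Section 10.3.1.3.
- Section 11.3.7.2 and the SAP tabulate worsening heart failure as its own line by treatment group.

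This changes recording and reporting only. It does not alter patient management or the wording of the stopping and dose-modification criteria. The cost is a wording amendment, a site memo and one additional table. The downside is a few more AE and SAE reports that reflect background disease, against which the placebo data give a comparison.

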10.3.1.1 Recording and Assessing Adverse Events

10.3.1.2 Description

All AEs spontaneously reported by the patient or reported in response to the open question from the study personnel: "*Have you had any health problems since you were last asked?*", or revealed by observation will be collected and recorded in the eCRF.

When collecting AEs, the recording of diagnoses is preferred (when possible) to recording a list of signs and symptoms (eg, anemia, not low hemoglobin). However, if a diagnosis is known and there are other signs or symptoms that are not generally part of the diagnosis, the diagnosis and each sign or symptom will be recorded separately.

Death is an outcome and not the name of the event.

10.3.1.3 Relationship to Study Treatment

The investigator should assess causality by answering either "yes" or "no" to the question "*Is there a reasonable possibility that the event may have been caused by the IMP/study medication?*"

The following factors can be used in consideration of causality assessment:

- Dechallenge/rechallenge: Did the event abate after study medication was reduced or interrupted? Did the event reappear after study medication was reintroduced?
- Temporal relationship and time to onset plausibility

- Confounding risk factors
- Amount and duration of study drug exposure
- Concomitant medications

10.3.1.4 Severity

Severity can be assessed as follows:

- Mild (awareness of sign or symptom, but easily tolerated)
- Moderate (discomfort sufficient to cause interference with normal activities)
- Severe (incapacitating, with inability to perform normal activities)
- Life-threatening (urgent intervention indicated)
- Fatal (event led to death)

It is important to distinguish between category (AE vs SAE) and intensity (mild, moderate, or severe) of AEs.

Severity is a measure of intensity, whereas seriousness is defined by the criteria stated above.

An AE of severe intensity need not necessarily be considered serious. For example, nausea that persists for several hours may be considered severe nausea but not an SAE. On the other hand, a stroke that results in only a limited degree of disability may be considered a mild stroke but would be an SAE.

All SAEs regardless of causality will be reported by the investigator or designee to MyoKardia or its designee per the reporting period defined in [Section 10.3.1](#) within 24 hours of knowledge of the event. All follow-up information for previously reported SAEs will also be reported to MyoKardia or its designee within 24 hours of knowledge. Deaths and SAEs occurring beyond this timepoint and considered related to study medication or study procedure must also be reported.

10.3.1.5 Pregnancy

Pregnancy, or if a partner of a male patient becomes pregnant during the study or for a period of 3 months after the male patient has taken the last dose of study medication, must be reported within the same timelines of an SAE. Pregnancies will be followed until final outcome and live births will be followed for 6 months after birth. SAE reporting instructions are provided in the Investigator Site File.

11 STATISTICAL METHODS

11.1 Determination of Sample Size

Part 1 is a single-ascending (oral) dose study and Part 2 is a multiple-ascending (oral) dose study to evaluate safety and tolerability of MYK-491. No formal statistical hypothesis testing will be performed.

In Part 1 (SAD), enrollment of at least 4 patients is planned for Cohort 1, with 1 patient randomized to each sequence of dose escalation and placebo administration. For Cohort 2, 4 to 8 patients will be enrolled and randomized to each sequence of dose escalation. There will be an option for the SRC to expand Cohort 1 or Cohort 2 to meet study objectives. Decision to expand or not the number of patients will be made by the SRC. Two additional patients may be enrolled as replacements for drop-outs in each cohort, so the maximum number of patients that may be enrolled will be approximately 32.

In Part 2 (MAD), enrollment of a total of a minimum of 24 patients is planned, with 8 patients enrolled the low-dose group (Cohort A), 8 patients enrolled in the medium-dose group (Cohort B) and 8 patients enrolled in the high-dose group (Cohort C). In addition, the planned size of additional optional Cohorts will be 8 patients each. The final total sample size for Part 2 will not exceed 96 patients if the SRC decides to expand one or more cohorts up to 24 patients. In addition, up to 2 additional patients may be enrolled per cohort as replacements for drop-outs or for patients non-evaluable for PK-PD at steady state.

Based on the study design, the sample is considered appropriate to explore tolerability and safety parameters, PK profile, and pharmacodynamic effects of MYK-491 in patients with heart failure.

